## **9.6.2. Analysis of Secondary Efficacy Endpoints**

### **9.6.2.1. 24-Week Double-blind Placebo-controlled Treatment Phase**

Descriptive statistics for change from Baseline, frequencies, or median time to event in efficacy measures will be summarized by visit for each treatment group, and for the treatment difference between each CC-90001 treatment group  $\pm$  SOC and the placebo treatment group  $\pm$  SOC. In addition, 95% CIs for the treatment differences will be provided to indicate the variability.

The analysis of most of the continuous secondary efficacy endpoints during the Double-blind Placebo-controlled Treatment Phase will be performed using an MMRM model in a manner similar to the primary analysis as specified in Section 9.6.1.

A random coefficient mixed effect model will be used to analyze the rate of decline of FVC. The usual FVC predictors, such as age, sex, height, and race, along with treatment and time interaction, will be included as fixed effects in the model, in which time will be treated as a numerical variable. In addition, intercept and slope of the linear relationship between FVC and time will be assumed to be subject-specific and treated as random coefficients. Comparisons of mean yearly decrease of FVC between treatment groups will be performed using appropriate contrasts.

A Cochran-Mantel-Haenszel (CMH) test will be used for the pair-wise comparisons of the proportions of subjects who experience disease progression at Week 24 between the two active treatment groups  $\pm$  SOC and the placebo  $\pm$  SOC. For the time to event data, such as time-to-first acute exacerbation and time to disease worsening, log-rank test will be provided by treatment, and a Kaplan-Meier estimate for the survival function will be provided for all the time to event data. For the time to event data (on-treatment time to death endpoint, time to first acute exacerbation and time to disease worsening while on treatment), Kaplan-Meier estimates for the survival function will be provided by treatment groups (CC-90001 200 mg PO QD  $\pm$  SOC, CC-90001 400 mg PO QD  $\pm$  SOC, and placebo  $\pm$  SOC). The number and

percentage of events within different time intervals during treatment will also be provided by treatment group.

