#### **9.6. Efficacy Analysis**

##### **9.6.1. Analysis of the Primary Efficacy Endpoint for the IPF Study**

A mixed-effect model of repeated measures (MMRM) will be used as the method for the primary efficacy analysis. The MMRM model will use the percent predicted FVC value as the dependent variable.

The MMRM model will include dose, time on treatment, current SOC (Yes/No), and interactions as fixed effects covariates. The model will also include the stratification factor applied to the non-SOC cohort, previous exposure to either pirfenidone or nintedanib (Yes/No), and Baseline percent predicted FVC value as fixed effects covariates. Time will be treated as a categorical variable in the MMRM model and will be considered as a repeated effect.

All post-baseline measurements up to Week 24 of percent predicted FVC values will be included in this analysis with no imputation of missing data other than that inherent in the MMRM model.

In addition to point estimates, 95% confidence intervals (CIs) for the differences calculated from the model (overall active treatment minus overall control, or active versus control within each cohort) of the least squares (LS) mean change from Baseline percent predicted FVC value and nominal p-values will also be provided, separately for each dose versus placebo comparison and also combining the 200 and 400 mg doses versus placebo comparison if both active treatment groups demonstrate efficacy. P-values and 95% CIs are considered descriptive measures of strength of association between dose and endpoint, rather than formal criteria to claim statistical significance.

In addition to the primary efficacy analysis of MMRM, non-parametric analysis of Rank-ANCOVA (Stokes, 2000) with a baseline FVC as a covariate for pair-wise comparisons with imputation of percent predicted FVC value for deaths to the worst rank will be applied as a

sensitivity analysis for the primary endpoint. Non-death discontinuation will be imputed in a different scheme; the details of the methods will be specified in the Statistical Analysis Plan.

To determine whether the treatment effect is consistent across various subgroups, the primary endpoint will be summarized by category of some classification variables observed at baseline including variables based on FVC (% predicted), age, time since first diagnosis of IPF, and prior therapy.

No multiplicity adjustment is planned for this study.

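### The FVC-slope model, rank-ANCOVA and log-rank test are stated without the randomization strata, the CMH test names none, and the final Week 24 analysis specifies no within-SOC-cohort result for slope, progression or time to event

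*Combined protocol and SAP*

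**What the plan says.** Section 3.1 stratifies randomization by concurrent SOC (Yes/No) and, for subjects without SOC, also by previous exposure to pirfenidone or nintedanib (Yes/No).

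Section 9.6.1 follows that design for the primary endpoint: "The MMRM model will include dose, time on treatment, current SOC (Yes/No), and interactions as fixed effects covariates". It adds the prior-exposure factor and baseline percent predicted FVC, and it provides contrasts within each cohort as well as overall.

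The other analyses are described differently:

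- **Rank-ANCOVA** (sensitivity analysis, Section 9.6.1): "with a baseline FVC as a covariate for pair-wise comparisons", with "imputation of percent predicted FVC value for deaths to the worst rank".
- **FVC slope** (Section 9.6.2.1): a random-coefficient model in which FVC predictors "such as age, sex, height, and race, along with treatment and time interaction, will be included as fixed effects".
- **Disease progression** (Section 9.6.2.1): "A Cochran-Mantel-Haenszel (CMH) test will be used for the pair-wise comparisons of the proportions of subjects who experience disease progression". No stratifying variable is given, and the groups are pooled over SOC.
- **Time to event** (Section 9.6.2.1): "log-rank test will be provided by treatment", with Kaplan-Meier curves for three groups pooled over SOC.

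Most other continuous secondary endpoints are to be "performed using an MMRM model in a manner similar to the primary analysis as specified in Section 9.6.1", so they inherit the strata and the cohort contrasts.

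**The concern.** When randomization is stratified on factors related to outcome, an analysis that ignores them overstates its standard error. Intervals are then a little too wide and tests a little conservative. The primary model avoids this; three of the supporting analyses, as stated, do not.

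The second issue is what gets reported. Section 9.3 gives the aim as estimating the effect in subjects with IPF with or without SOC, and it assumes different effects in the two cohorts. Section 9.9.3 says the secondary analyses help inform dose selection. For slope, progression and time to event, the final Week 24 plan gives only results pooled over two cohorts whose effects the sponsor expects to differ. A reader of those results could not see whether they hold both with and without SOC.

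**Working it through.** **1. Terms named for each analysis, final Week 24 analysis**

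| Analysis | SOC | Prior exposure | Cohort result |
|---|---|---|---|
| Primary MMRM (9.6.1) | yes, with interactions | yes | yes |
| Most continuous secondaries (9.6.2.1) | by reference to 9.6.1 | by reference | by reference |
| Rank-ANCOVA (9.6.1) | not named | not named | none |
| FVC slope (9.6.2.1) | not named | not named | none |
| Log-rank (9.6.2.1) | not named | not named | none |
| CMH (9.6.2.1) | strata not named | strata not named | none |

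The subgroup summaries in Section 9.6.1, which include prior therapy, cover the primary endpoint only.

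**2. The plan's own power figure.** Inputs from Section 9.3: 55 per arm, SD 5, two-sided alpha 0.1, difference 2.2. SE = 5 × √(2/55) = 0.953. Power is 74.2% by the noncentral t and 74.6% by the normal approximation, so the stated 75% reproduces. With 25 SOC and 30 non-SOC subjects per arm (Section 3.1), the unrounded mix is (30 × 3 + 25 × 1.3)/55 = 2.227, which gives 75.1%. That is the reference below.

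**3. Cost of leaving SOC out.** The proxy is Week 24 change in percent predicted FVC, not the mL slope model. The SD of 5 is taken as the within-cohort SD. Let D be how many points less the SOC cohort declines on placebo than the non-SOC cohort. The documents give no value, so D = 1, 2 and 3 are assumptions. With effects of 3 and 1.3, the corresponding gap on active treatment is D − 1.7.

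- SOC share p = 25/55; p(1 − p) = 0.2479.
- Inflation of the estimated variance = 0.2479 × [D² + (D − 1.7)²]/(2 × 25).
- Interval ratio r = √(1 + inflation).
- Under stratified randomization only the estimated SE inflates; the estimator's true SE stays at 0.953. So power ≈ Φ(2.227/0.953 − 1.659 × r), where 1.659 is the t critical value on 108 df and 2.227/0.953 = 2.336 before rounding.

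| D | Inflation | Intervals wider by | Power (reference 75.1%) |
|---|---|---|---|
| 1 | 0.0074 | 0.4% | 74.9% |
| 2 | 0.0203 | 1.0% | 74.5% |
| 3 | 0.0530 | 2.6% | 73.7% |
| −1 | 0.0411 | 2.0% | 74.0% |
| −2 | 0.0877 | 4.3% | 72.8% |
| −3 | 0.1542 | 7.4% | 71.0% |

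A simulation of 200,000 trials for D = 1, 2 and 3 gave 74.8%, 74.6% and 73.8%, in agreement to about 0.1 point. Negative D means the SOC cohort declines more on placebo. The cost is then larger because the gap on active treatment, D − 1.7, grows in size.

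I give no power figures for the rank-ANCOVA, CMH or log-rank test. They would need a death rate, event risks and effect sizes that the documents do not state.

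**4. Precision of cohort results for progression.** 95% half-width of a risk difference = 1.96 × √(2q(1 − q)/n), with an assumed risk q of 20%, 30% or 40% in both arms:

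- Non-SOC, n = 30 per arm: 20.2, 23.2, 24.8 percentage points.
- SOC, n = 25 per arm: 22.2, 25.4, 27.2 percentage points.

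**The case against.** The strongest reply is that the protocol is only an outline. Section 9.1 leaves details to a separate SAP, the slope list is introduced as examples, a by-treatment log-rank test can still be stratified, and a CMH test normally is. This stands: a reader might infer that the analyses will be run without the strata, and the documents do not show that. For the CMH test, the point is missing detail only. What remains is that the stated lists leave out the factors the primary model names.

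Three other tempting readings also go too far:

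- **That cohort results are absent throughout.** Section 9.8 describes the interim analyses as similar to those in Sections 9.6.1 and 9.6.2, has the second interim evaluate efficacy in SOC subjects, and lets discontinuation of a treatment group be decided by cohort. Cohort looks may therefore occur at the interims. The gap is clear only for the final Week 24 analysis.
- **That FVC in mL is wholly uncovered.** Absolute change in mL plausibly falls under the MMRM wording, with strata and cohort contrasts. Only the slope version lacks them.
- **That adding strata to the rank-ANCOVA would let any disagreement with the MMRM be traced to deaths and dropouts.** It would not. The two also differ in using ranks rather than means, in the repeated-measures structure and in imputation. Matching the covariates removes one difference among several.

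It is also fair to say the consequence is low: "P-values and 95% CIs are considered descriptive measures of strength of association between dose and endpoint", and omitting the strata does not inflate type I error.

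**Conclusion.** The point holds as a specification gap of low consequence. Three analyses as stated leave out both randomization factors, a fourth names no strata, and slope, progression and time to event have no specified SOC-cohort result at the final Week 24 analysis.

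The efficiency loss is small and conservative: on the proxy, about 0.4% to 2.6% in interval width for placebo gaps of 1 to 3 points favouring SOC, and 2.0% to 7.4% for gaps of the same size in the other direction. These figures rest on the assumed gaps, on SD 5 being the within-cohort SD, and on a Week 24 change standing in for the slope model. The larger benefit of acting is consistency with the primary model and a view of each cohort, though the cohort estimates will be imprecise. This is a worthwhile improvement, not a threat to the trial's conclusions.

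**What to change.** In the SAP, before unblinding:

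1. Define one three-level stratum: SOC; non-SOC with prior pirfenidone or nintedanib exposure; non-SOC without.
2. Slope model: add stratum and stratum-by-time. Obtain cohort slope differences from a version with SOC-by-treatment-by-time and its lower-order terms.
3. Log-rank and CMH tests: stratify by the same variable, collapsing to SOC Yes/No if cells are sparse.
4. Rank-ANCOVA: add the stratum, keeping ranks taken over all subjects, so that its baseline factors match those of the MMRM.
5. At the final Week 24 analysis, report slope, progression and time-to-event results by SOC cohort with 95% intervals. Label them descriptive and state their imprecision. A stratified test alone does not supply these, because it still yields one pooled result.

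The cost is SAP wording and a few extra outputs. The strata are already recorded at randomization, and no data collection or trial conduct changes.

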### 1.6.3. Rationale for Selecting FVC as the Primary Endpoint

Change in FVC was selected as the primary endpoint because of its widespread clinical use and the clinical relevance of irreversible loss of lung function. Change in FVC is currently accepted by health authorities as a primary endpoint in IPF trials in part because it is a reliable, responsive

measurement. Deterioration in FVC  $\geq$  10% from baseline over 6 months has been shown to predict mortality in IPF patients (du Bois, 2011).

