### 8.1.2. Permitted Medications to Treat New or Worsening Shortness of Breath

Medications, such as prednisone (> 12.5 mg/day or equivalent), azathioprine, and cyclophosphamide can be initiated or increased at Investigator's discretion for the treatment of an exacerbation. Subjects may be given supplemental oxygen to alleviate hypoxemia. These drugs should be discontinued at the Investigator's discretion upon resolution of the exacerbation. If an exacerbation has not improved within 6 weeks or a subject has shown signs of further clinical decline despite adequate treatment, the subject should be discontinued from study IP and enter the Post-treatment Observational Follow-up Phase, as per the Table of Events, [Table 5](#).

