### 9.7.2. Disease Progression

A subject will have met the criteria for disease progression when one or more of the following events have occurred:

- Death from respiratory failure, or
- Absolute decrease of  $\geq 10\%$  from baseline in percent predicted FVC at two consecutive evaluations at a minimum of 4 weeks between evaluations, or
- Decrease from baseline of  $\geq 50$  meters in 6MWT distance (in the absence of a readily explainable cause, such as injury or trauma), or
- Unexplained worsening hypoxemia (an absolute decrease from baseline of 4% or more in SpO2).

Subjects who experience an absolute decrease of  $\geq 10\%$  from baseline in percent predicted FVC at two consecutive evaluations at a minimum of 4 weeks between evaluations must be discontinued from the study IP and enter the Post-treatment Observational Follow-up (see Section 11.1). Example: a subject whose FVC decreases from 50% predicted at Visit 2 to 40% predicted at Visits 4 and 5 must be discontinued from the study. Whether to discontinue a subject from study treatment who experiences: 1) a decrease from baseline of  $\geq 50$  meters in 6MWT distance (in the absence of a readily explainable cause, such as injury or trauma), or 2) a new or worsening hypoxemia (an absolute decrease from baseline of 4% or more in SpO2), is at the Investigator's discretion.

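### On-treatment Kaplan-Meier curves for death overstate survival in each arm, because a lung-function decline that the protocol links to mortality forces subjects off drug

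*Combined protocol and SAP*

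**What the plan says.** Section 9.6.2.1 covers the time-to-event outcomes of the 24-week placebo-controlled phase in two sentences. The first is general and has no on-treatment limit. It promises that "a Kaplan-Meier estimate for the survival function will be provided for all the time to event data". It also plans a log-rank test by treatment and gives first acute exacerbation and disease worsening as its examples; death is not among them. The second sentence limits the by-arm curves to time on drug: "on-treatment time to death endpoint, time to first acute exacerbation and time to disease worsening while on treatment".

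Four other places bear on this:

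- Section 9.7.2: subjects with a confirmed absolute FVC fall of 10 points or more in percent predicted "must be discontinued from the study IP and enter the Post-treatment Observational Follow-up". Stopping for a fall in walk distance or oxygen saturation "is at the Investigator's discretion".
- Section 8.1.2: for an exacerbation unimproved within 6 weeks, or further decline despite treatment, "the subject should be discontinued from study IP and enter the Post-treatment Observational Follow-up Phase". This is worded as a should, not a must.
- Section 1.6.3: FVC deterioration of 10% or more "over 6 months has been shown to predict mortality in IPF patients".
- Sections 3.1, 6.3 and 10.1: follow-up after stopping lasts 4 weeks. Adverse events are recorded to 28 days after the last dose, and after that only serious events suspected of being drug-related.

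The available text does not say whether on-treatment ends at the last dose or 28 days later, and gives no censoring rule.

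**The concern.** A Kaplan-Meier curve is valid only if subjects censored at a given time have the same later risk as those still followed. The mandatory FVC rule breaks this for death. It removes subjects from treatment because of a decline that the protocol itself treats as a warning of death. If death is observed only while on drug, the subjects at highest risk leave the risk set just before their risk is realised, and the curve describes the healthier remainder.

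Each arm's survival would then look better than it was. Arms may also differ in how often subjects stop: Section 1.7 describes mainly gastrointestinal adverse events on CC-90001, and Section 11.2 ends treatment for confirmed transaminase elevation. The curves would then be hard to compare as well as too high.

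**Working it through.** **Figures in the plan.** There is no event rate, event count or power for death. The one stated power, 75% for the primary endpoint (Section 9.3: 55 per arm, difference 2.2, SD 5, two-sided alpha 0.10), reproduces. The standard error is 5 × √(2/55) = 0.953; 2.2/0.953 = 2.307; 2.307 − 1.645 = 0.662, giving 74.6% (74.2% with the noncentral t). It says nothing about death.

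**Follow-up gap.** In the example in Section 9.7.2 the decline is seen at Visits 4 and 5, that is, Weeks 4 and 8. Drug stops at about Week 8 and follow-up ends at about Week 12, so 24 − 8 − 4 = 12 weeks are unobserved. Stops at Weeks 12, 16 and 20 leave 8, 4 and 0 weeks.

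**Size of the bias.** The inputs are assumptions. Let T = 24 weeks with constant hazards, and define:

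- p_d = probability of a forced-stop decline by Week 24; λ = −ln(1 − p_d)/T
- p_0 = probability of death by Week 24 at the pre-decline hazard; h_0 = −ln(1 − p_0)/T
- r = multiplier of the death hazard after the decline; h_1 = r·h_0
- a = λ + h_0

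True survival at Week 24 is

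S = exp(−aT) + λ·exp(−h_1·T) × [1 − exp(−(a − h_1)T)]/(a − h_1).

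A Kaplan-Meier curve censored at the stop estimates 1 − p_0. The overstatement is (1 − p_0) − S.

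*Worked case:* p_d = 10%, p_0 = 4%, r = 6.

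1. λT = 0.1054, h_0·T = 0.0408, h_1·T = 0.2449, aT = 0.1462.
2. First term: exp(−0.1462) = 0.8640.
3. Second term: 0.1054 × 0.7828 × 1.0511 = 0.0867.
4. S = 0.9507, so true mortality is 4.93% against 4.00% on the curve: 0.93 points.

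The full grid gives survival overstated, in percentage points. The first number is for censoring at the stop. The second is for censoring 28 days later, from simulation of 1,000,000 subjects.

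| p_d | p_0 | r = 3 | r = 6 | r = 10 |
|---|---|---|---|---|
| 5% | 2% | 0.10 / 0.07 | 0.24 / 0.17 | 0.42 / 0.29 |
| 5% | 4% | 0.19 / 0.11 | 0.46 / 0.36 | 0.79 / 0.55 |
| 10% | 2% | 0.20 / 0.12 | 0.49 / 0.30 | 0.85 / 0.57 |
| 10% | 4% | 0.39 / 0.27 | 0.93 / 0.63 | 1.59 / 1.03 |
| 20% | 2% | 0.41 / 0.26 | 0.99 / 0.66 | 1.74 / 1.13 |
| 20% | 4% | 0.79 / 0.55 | 1.90 / 1.27 | 3.24 / 2.11 |

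With r = 1 the overstatement is zero (simulation error in the 28-day figures is up to 0.03 points). In the last cell true mortality is 7.2%, against 4.0% on the curve, or 5.1% with the 28-day window. In an arm of 55 that is 55 × 0.0324 = 1.8 deaths missed.

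**Worsening and exacerbation.** Section 9.7.2 opens its list with "A subject will have met the criteria for disease progression when one or more of the following events have occurred", and the FVC fall that forces the stop is on that list. If worsening means progression in this sense, the forced stop is itself the event and censors nothing. Likewise, a stop for an unresolved exacerbation comes after the first exacerbation has been counted.

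**The case against.** A labelled on-treatment curve is a legitimate summary, and other planned outputs record deaths around the stop. Disease progression, which includes death from respiratory failure, runs from Baseline through Week 24 and is compared as a proportion, with efficacy analysed mainly in the FAS by randomised arm. The Rank-ANCOVA gives deaths the worst rank. Safety summaries include the follow-up visit, deaths are adjudicated, and an unblinded DMC reviews safety. The general sentence in Section 9.6.2.1 promises Kaplan-Meier estimates without an on-treatment limit. Section 9.1 defers detail to a separate SAP, which is not in the text reviewed and may define censoring.

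Most of this stands as a limit on severity. It does not remove the point, because an unrestricted curve needs deaths to Week 24, and collection largely ends 28 days after the last dose. The exceptions are serious events suspected of being drug-related and, under Section 10.2.6, serious events still open when the subject leaves the study. A SAP can state a censoring rule but cannot recover deaths that were never recorded.

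A reader might infer more than the documents support:

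- **That the worsening and exacerbation curves are biased in the same way.** For stops triggered by those events they are not, as shown above. Disease worsening is undefined in the available text, so other stops could still matter. A forced FVC stop could also cut short observation of a later first exacerbation, but no statement in the documents allows its effect to be sized.
- **That every death after stopping is discarded.** No visible rule says so, and a 28-day window would retain some.
- **That the treatment comparison is biased in a known direction.** That depends on stop rates and reasons by arm, which the documents do not give.

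**Conclusion.** The point holds for death. Given the mandatory FVC stop and the protocol's own statement on mortality, ending observation of death at drug stop overstates survival in each arm. The overstatement at Week 24 is about 0.1 to 3.2 percentage points (about 0.1 to 2.1 with a 28-day window) if the hazard rises 3- to 10-fold after the decline, and zero if it does not rise.

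This rests on assumed forced-stop rates of 5 to 20%, background mortality of 2 to 4%, constant hazards, and an on-treatment window ending at the last dose or 28 days after it. The cited mortality finding is for FVC deterioration over 6 months. The stop rule uses two consecutive falls in percent predicted, so the match is close but not exact.

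Deaths are few (about 1 to 4 among 55 per arm on these assumptions), and the primary analysis is unaffected. The change is worth making because it is cheap and the missing deaths cannot be recovered later.

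**What to change.** 1. Make time to death from randomisation to Week 24, by randomised arm in the FAS and regardless of drug status, the main death analysis.
2. Collect vital status at Week 24 for every subject who stops drug early.
3. Include deaths and exacerbations already collected up to 28 days after the last dose.
4. Keep the on-treatment curves as supportive. State when on-treatment ends, what censors a subject, and what disease worsening means.

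The cost is a short protocol change for one vital-status contact, one added analysis and some SAP wording. No stopping rule changes. A side benefit is that a death after early stopping would be classified correctly in the Rank-ANCOVA sensitivity analysis, which handles deaths and other discontinuations differently (Section 9.6.1). Following exacerbation and worsening to Week 24 off drug would need extra visits for spirometry, walk tests and oximetry, and is not part of this request.
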